#### 9.3.2 Outcomes

EMR-based clinical characteristics that are typically used as covariates will be treated as outcomes in this validation study. Unless otherwise noted, all of these outcomes will have an indicator for being recorded in EMR (Present, Y/N). Index date is the date of dabigatran or

warfarin initiation. All characteristics will be assessed prior and including the medication initiation date (index date). The characteristics presented in [Table 1](#) reflect likely availability in the EMR.

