**Table 1 Outcome definitions**

Outcome	Definition	Present	Categories if present
Primary			
Obesity	Calculated BMI >30 or recorded "obesity"	Y/N	Obese, not-obese based on note of obesity or recorded BMI>30.
Smoking	Any note on smoking	Y/N	Current & past combined and nonsmoker & not noted combined.
Alcohol consumption	Any note on alcohol use	Y/N	Alcohol use (any); No use
Abnormal renal function	Any note of: Dialysis, renal transplant Serum Creatinine >1.3 mg/dL	Y/N	
Bleeding history or predisposition	Any note of: Major bleeding requiring hospitalization or blood transfusion or causing a decrease in hemoglobin level of > 2 g/L	Y/N	
Renal function	Estimated GFR closest to index dispensing	Y/N	The value
Serum Creatinine	Closest to the index date	Y/N	The value
Abnormal liver function	Any note of: Liver disease, cirrhosis, Active hepatitis C Active hepatitis B Active hepatitis A AST/ALT >3X upper limit of normal Absence of any note would be considered as absence of the disease	Y/N	

[figure not shown]
Table 1 (cont'd) Outcome definitions

[figure not shown]
Outcome	Definition	Present	Categories if present
Secondary			
Duration of atrial fibrillation	Years/months prior to initiation of dabigatran/warfarin	Y/N	Number of months prior to index date for the earliest note
History of adherence	Any note of patient adherence/lack thereof in EMR	Y/N	Non-adherent Adherent
History/duration of hypertension	Any note of: Hypertension SBP >120 mmHg Hypertension drugs	Y/N	Number of months prior to index date for the earliest date
Uncontrolled Hypertension (for HASBLED)	SBP >160 mmHg using the most recent information prior to index date	Y/N	
History/duration of CHF	Any note of: CHF	Y/N	Number of months prior to index date for the earliest note
Prior TIA	Any note of TIA	Y/N	Also, number of months prior to index date if noted
Diabetes	Any note of: Diabetes Absence of any note of diabetes will be considered as absence of the disease	Y/N	
Hyperlipidemia	Any note of; Hyperlipidemia, dyslipidemia, LDL>130 mg/dl		
HAS Bled Score	As recorded (if recorded) or calculated from EMR data. [REDACTED]	Recorded/ calculated /none	The value
Use of antiplatelets or NSAIDs (needed for HASBLED)	Use of aspirin, clopidogrel, prasugrel, ticagrelor or NSADs (within 1 month or on the index date)	Y/N	
INR	Closest to the index date	Y/N	The value

[figure not shown]

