## **9.5 STUDY SIZE**

[figure not shown]
This study will identify covariates that represent potential confounding variables among dabigatran and warfarin users within a sampled population. The ability to identify a covariate and the precision for estimating potential confounding from the covariate will depend on the numbers of patients from whom electronic medical record data is extracted, and features of the covariate itself, such as how certain it is to be recorded in the medical record and whether binary (yes/no) or other.

The PS-matched dabigatran and warfarin initiators during Oct 2010– December 2013 period are approximately 20,000 each. Assuming that 5.5% of this study group will be linked to EMR, the EMR-linked subset up to Dec 2013 will consist of approximately 1100 patients in each exposure group.

The precision of estimated prevalence for a covariate obtained from the EMR depends on the prevalence of the covariate, and the sample size. With 10,000 dabigatran initiators, this study will estimate a patient characteristic that has a 10% prevalence with considerable precision (the 95% confidence interval will be 9.4% to 10.6%) ([Table 7](#)). A characteristic not captured in claims, but present in the medical record with a prevalence of 10% to 20% is plausibly a confounding variable and so this table enumerates characteristics with these prevalences. The table has not been extended below 10% since such lower prevalence characteristics have progressively less ability to produce meaningful confounding, so that while the study will have less precision to estimate such a characteristic, validation of the presence for such a low prevalence characteristic becomes unnecessary. At the other end of the range presented in the table, a characteristic with a prevalence above 20% will be identified with even greater precision, so that it also does not need to be depicted in the table.

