**Table 8 Association between claims-based covariates and EMR linkage.**

Claims-based covariate	Dabigatran initiators		Warfarin initiators	
	N=		N=	
	Linked	Not linked	Linked	Not linked
Proportion (N)				
Age				
Age category 18-35				
Age category 36-64				
Age category 65-74				
Age category 75+				
Sex				
...				

*Objective 1: Descriptive*

The analyses for this objective will occur within the subpopulation of individuals with linked EMR data and will focus on describing the EMR-based clinical characteristics for the dabigatran and warfarin initiators. This table will provide an evaluation of the association between the EMR clinical characteristics and initiation of dabigatran or warfarin. [REDACTED]

The prevalence of each category for categorical characteristics and the mean and standard deviation for continuous characteristics will be calculated (as shown in the example [Table 9](#)). This analysis will aid in identifying EMR characteristics that are unbalanced across exposure groups and are therefore potential unmeasured confounders after PS matching.

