**Table 9** **EMR clinical characteristics in matched dabigatran and warfarin initiators**

EMR clinical characteristic	Dabigatran initiators	Warfarin initiators
	N=	N=
[REDACTED]		
Smoking		
Alcohol consumption		
Obesity		
...		

[figure not shown]
Note: anticoagulant initiation [REDACTED] are based on claims data

We will seek to define variables derived from the EMR in a manner that reduces missingness. Accordingly, most variables will be defined as presence or non-presence in the EMR, which we will take as a proxy of being medically-recognized. For example, if smoking is noted in the medical record, it will be recorded as present, if it is not present, it will be assumed that the patient does not smoke. We will also evaluate the patterns of missing data in the EMR clinical characteristics.

Objective 2: Prediction Rule

[figure not shown]
Within the EMR linked subpopulation, a prediction model will be developed [REDACTED] with particular focus on covariates that are found to represent potentially important unmeasured confounding in the primary analysis. Specifically, a logistic regression model (potentially a multinomial logistic regression, depending on the number of categories for the EMR characteristic) will be estimated [REDACTED] that uses the EMR covariate as the model outcome and all available claims-based covariates as predictors. [REDACTED]

For [REDACTED] continuous EMR-based characteristic, a linear regression model will be estimated. Coefficients from these models will be reported as well as prediction accuracy, defined by the R2 statistic.

*Objective 3: Potential Unmeasured Confounding Assessment*

To assess the potential for confounding, we will conduct a series of logistic regression analyses that predict exposure (dabigatran versus warfarin) from covariates.

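### The broad Table 1 rule for history of hypertension (any systolic reading above 120 mmHg, or any hypertension drug, ever) is likely to misclassify patients and to mask or distort an imbalance between the groups

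*Combined protocol and SAP*

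**What the plan says.** Section 9.3.2 treats EMR characteristics as outcomes. Table 1 lists history/duration of hypertension among the secondary outcomes, with the definition "Any note of: Hypertension SBP >120 mmHg Hypertension drugs". The row sets no minimum number of readings, no averaging, and no indication for the drugs. Its second part is a duration: "Number of months prior to index date for the earliest date".

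The time window is open at the early end: "All characteristics will be assessed prior and including the medication initiation date (index date").

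Other Table 1 rows are narrower. Uncontrolled hypertension is "SBP >160 mmHg using the most recent information prior to index date". The CHF and TIA rows need a note of the condition itself.

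Section 9.7.1 gives the use. Under Objective 1, prevalences or means are set side by side by exposure group: "This analysis will aid in identifying EMR characteristics that are unbalanced across exposure groups". It adds that "most variables will be defined as presence or non-presence in the EMR". Objective 3 uses logistic regression of exposure on covariates.

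**The concern.** An any-entry-ever rule with a low cut takes in people who do not have hypertension, and takes in more of them the more often blood pressure was recorded. Three things follow.

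- A true difference in hypertension shrinks, because the misclassified patients are added to both groups.
- If one group has denser or longer records, the rule can produce a difference that is not hypertension.
- Duration starts at the earliest qualifying entry. It can never be shorter than the time since the first hypertension note, and is longer whenever an isolated reading or drug entry came first. It therefore partly tracks how far back the record goes.

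The study exists to judge whether claims-based matching leaves clinical characteristics unbalanced. A diluted or distorted row could mislead that judgement in either direction.

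**Working it through.** **Group size.** Section 9.5 states "The PS-matched dabigatran and warfarin initiators during Oct 2010– December 2013 period are approximately 20,000 each" and assumes 5.5% linkage: 20,000 × 0.055 = 1,100, which reproduces its figure of 1,100 per group. The abstract gives 15,000 per group: 15,000 × 0.055 = 825. Both are used below. The documents give no expected prevalence of hypertension, so there is no plan figure for this outcome to reproduce.

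**Assumptions (not in the documents).** True prevalence is 80% in one group and 70% in the other. Every truly hypertensive patient qualifies. Non-hypertensive patients have mean systolic pressure m of 115 or 122 mmHg, with between-person SD 13 and within-person SD 10. Each has k readings, independent given the person's own mean. The drug route is left out; it can only raise f.

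**Formulas.**
- Share of non-hypertensive patients with at least one reading above 120: f = 1 − E[Φ((120 − X)/10)^k], with X ~ N(m, 13²).
- Observed prevalence: a = 0.80 + 0.20f and b = 0.70 + 0.30f, so the observed difference is 10 × (1 − f) points.
- 95% half-width: 1.96 × √{[a(1 − a) + b(1 − b)]/n}.
- Odds ratio: (a/b) × (1 − b)/(1 − a) = (a/b) × 1.5, because (1 − b)/(1 − a) = 0.30/0.20 for every f below 1.

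With no misclassification (f = 0) the difference is 10 points, the half-width is 4.2 points at 825 and 3.6 at 1,100, and the odds ratio is 1.71.

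| m | k | f | Observed, % | Difference | Half-width, 825 | Half-width, 1,100 | OR |
|---|---|---|---|---|---|---|---|
| 115 | 1 | 0.38 | 87.6 v 81.4 | 6.2 | 3.5 | 3.0 | 1.61 |
| 115 | 3 | 0.59 | 91.8 v 87.7 | 4.1 | 2.9 | 2.5 | 1.57 |
| 115 | 6 | 0.70 | 94.0 v 91.0 | 3.0 | 2.5 | 2.2 | 1.55 |
| 115 | 12 | 0.79 | 95.7 v 93.6 | 2.1 | 2.2 | 1.9 | 1.53 |
| 122 | 1 | 0.55 | 91.0 v 86.5 | 4.5 | 3.0 | 2.6 | 1.58 |
| 122 | 3 | 0.76 | 95.1 v 92.7 | 2.4 | 2.3 | 2.0 | 1.54 |
| 122 | 6 | 0.84 | 96.9 v 95.3 | 1.6 | 1.9 | 1.6 | 1.52 |
| 122 | 12 | 0.90 | 98.0 v 97.1 | 1.0 | 1.5 | 1.3 | 1.52 |

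One line in full (m = 122, k = 3, n = 825): a = 0.80 + 0.20 × 0.757 = 0.951; b = 0.70 + 0.30 × 0.757 = 0.927; difference 10 × 0.243 = 2.4 points; half-width 1.96 × √[(0.951 × 0.049 + 0.927 × 0.073)/825] = 2.3 points.

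With 1 or 3 readings the difference exceeds the half-width at both group sizes. With 12 readings and m = 122 it does not at either size. With 12 readings and m = 115 it is borderline.

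**False imbalance.** Suppose both groups truly have 75%, one with 3 readings per patient and the other with 12 (a deliberately wide contrast). At m = 122 the rule gives 0.75 + 0.25 × 0.757 = 93.9% against 0.75 + 0.25 × 0.902 = 97.5%. At m = 115 it gives 89.7% against 94.7%. The gap of 3.6 to 4.9 points comes from record density alone.

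**The case against.** The strongest reply has four parts.

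- **The stronger reading is not supported.** A reader might infer that nearly every patient qualifies, so that the row would report balance whatever the truth. The documents give no blood pressure distribution, number of readings, look-back length or hypertension prevalence, so the first part is an inference. The second fails even under the assumptions above: with few readings a 10-point difference stays visible, and the odds ratio, the scale that the Objective 3 logistic models work on, cannot fall below 1.5 in this scenario. This stands. It limits the concern to dilution and lost precision, mainly when records hold many readings.
- **Uncontrolled hypertension is a separate row**, using the latest reading and a cut of 160 mmHg, and it is the HAS-BLED hypertension item in Table 2. This stands, so the bleeding score does not depend on the broad rule. That row captures current marked elevation, though, and does not replace history.
- **The drug route may be narrower than it looks.** No drug list or indication rule is visible, and its effect cannot be sized from the documents. This stands, and it is why the figures leave that route out.
- **Duration from the earliest entry is also used for atrial fibrillation and CHF, and any dating is limited by where the record starts.** This is true, so it would be wrong to infer that duration measures record length and nothing else. But the CHF row depends on a note of the condition; here an isolated reading can start the clock.

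**Conclusion.** The concern holds in a limited form. As written, the rule is likely to classify many non-hypertensive patients as hypertensive, to mask or distort a true imbalance, and to make duration partly reflect length of EMR history.

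Under the stated assumptions a true 10-point difference shrinks to about 4.1 to 2.4 points with 3 readings and to 2.1 to 1.0 points with 12, before the drug route. At 825 per group the intervals still exclude zero with 3 readings, only just at the higher mean, but not with 12. The odds ratio is only mildly attenuated, from 1.71 to about 1.5 to 1.6.

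The prevalences, the blood pressure mean and SDs, the number of readings and their conditional independence are all assumed. This is one secondary outcome among several. The change is worth making because it is cheap, not because the row is uninformative.

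**What to change.** In Table 1:

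- Make a recorded hypertension diagnosis or note the main definition, and date duration from the earliest such note.
- Report the route through a reading above 120 mmHg, the drug route and the current combined definition as separate or sensitivity rows.
- Report systolic pressure closest to the index date as a continuous value, as Table 1 already does for serum creatinine and estimated GFR.
- Report the number of systolic readings and the length of EMR history by exposure group, so that an artefact of record density can be recognised.

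The cost is Table 1 wording, extraction code and a few extra rows in the Table 9 output. The downside is that the main row misses some treated patients who have no recorded diagnosis; the combined sensitivity row still captures them.

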Variables:	
Patient characteristics derived from insurance claims (claims-based covariates)
 
This study will characterize patients initiating oral anticoagulant medications with respect to select characteristics, some of which might be reflected differently in claims data compared to electronic medical records prior to and including the date of initiation. These characteristics from EMR data are usually treated as covariates but will be considered outcomes in this validation study.
 
These characteristics include:
 
Primary Outcomes
 
 
• Obesity
 
• Smoking
 
• Alcohol consumption
 
• Abnormal renal function
 
• Bleeding history or predisposition
 
• Renal function (estimated GFR)
 
• Serum Creatinine
 
• Abnormal liver function
 
 
Secondary Outcomes
 
 
• Duration of atrial fibrillation
 
• History of adherence
 
• History/duration of hypertension
 
• Uncontrolled Hypertension (for HAS-BLED)
 
• History/duration of CHF
 
• Prior TIA
 
• Diabetes
 
• Hyperlipidemia
 
		

Name of company: Boehringer Ingelheim			
Name of finished medicinal product: Pradaxa® (Dabigatran etexilate), or warfarin			
Name of active ingredient: Dabigatran etexilate or warfarin			
Protocol date: 02 November 2016	Study number: 1160.219	Version/Revision: 1.0	Version/Revision date:
Variables:	
 
HAS-BLED Score
 
Use of antiplatelets or NSAIDs (needed for HAS-BLED)
 
		
Data sources:	This study will be conducted within MarketScan data linked to electronic medical records.		
Study size:	
Study cohort: approximately 15,000 dabigatran initiators PS-matched to 15,000 warfarin initiators
 
EMR-linked subset: approx. 5.5% of the study cohort.
		

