#### 9.3.2.2 Secondary outcomes

- Duration of atrial fibrillation
- History of adherence
- History/duration of hypertension
- Uncontrolled Hypertension (for HAS-BLED)
- History/duration of CHF
- Prior TIA
- Diabetes
- Hyperlipidemia
- HAS-BLED Score
- Use of antiplatelets or NSAIDs (needed for HAS-BLED)

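### Blood pressure control is listed only as a yes/no flag at SBP >160 mmHg; also reporting the latest systolic value would detect group differences of 2 to 3 mmHg far better, at almost no cost

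*Combined protocol and SAP*

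**What the plan says.** Table 1 takes the latest systolic reading and turns it into a yes/no item: "SBP >160 mmHg using the most recent information prior to index date". The column for categories or values is empty in that row. Section 9.3.2.2 lists the item as a secondary outcome, and its label ties it to HAS-BLED, where Table 2 gives uncontrolled hypertension one point.

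The only other readable use of systolic pressure is in the Table 1 row for history and duration of hypertension. There, any note of SBP above 120 mmHg is one of three triggers, and the output is a yes/no plus months since the earliest date.

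Other measurements are treated differently. Serum creatinine and INR are taken as "Closest to the index date", eGFR is taken nearest the index dispensing, and all three are kept as values. Creatinine is also cut at 1.3 mg/dL for the abnormal renal function item, so it appears both ways.

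For Objective 1, section 9.7.1 plans prevalences for categorical characteristics, and says that "the mean and standard deviation for continuous characteristics will be calculated". The purpose is to find EMR characteristics that are unbalanced between the drug groups after matching. No test or balance threshold is visible. Of the Objective 3 specification, one sentence is readable: exposure will be modelled on covariates by logistic regression.

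**The concern.** Objectives 1 and 3 look for clinical characteristics that are poorly captured in claims and differ by drug. A measured systolic pressure is a natural candidate. A cut at 160 mmHg uses only the upper tail, so a shift of the whole distribution appears as a small change in a small proportion.

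Section 9.5 adds to this. It argues that characteristics below 10% prevalence have progressively less scope to confound and need not be validated. Under the assumptions below, only about 2% to 8% of the reference group exceed 160 mmHg, so a reader applying that argument could set the flag aside although the underlying measurement is continuous. At stake is whether a modest difference in pressure control that the linked subset could detect becomes visible.

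**Working it through.** **1. Group sizes (from the plan).** Section 9.5 states that "The PS-matched dabigatran and warfarin initiators during Oct 2010– December 2013 period are approximately 20,000 each" and that "the EMR-linked subset up to Dec 2013 will consist of approximately 1100 patients in each exposure group". Check: 20,000 × 0.055 = 1,100, which reproduces it. The abstract has "approximately 15,000 dabigatran initiators PS-matched to 15,000 warfarin initiators" and the same 5.5% linkage: 15,000 × 0.055 = 825. The two cohort sizes do not agree with each other, so both are carried as a range.

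**2. Assumptions (not in the documents).** SBP is normal with the same SD in both groups, reference mean 128 or 132 mmHg and SD 16, 18 or 20 mmHg. Every linked patient has a reading. The test is two-sided at 5%.

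**3. Share above the cut.** p = 1 − Φ((160 − mean)/SD). With mean 132 and SD 18: 28/18 = 1.556, so p₁ = 6.0%. With a 3 mmHg shift: 25/18 = 1.389, so p₂ = 8.2%.

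**4. Power on the value.** Φ(δ/(SD·√(2/n)) − 1.96).
- n = 1,100: SE = 18·√(2/1,100) = 0.768; 3/0.768 = 3.91; Φ(1.95) = 97%.
- n = 825: SE = 0.886; 3/0.886 = 3.39; Φ(1.43) = 92%.

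**5. Power on the flag.** Φ((|p₂ − p₁| − 1.96·SE₀)/SE₁), with SE₀ pooled and SE₁ unpooled.
- n = 1,100: (0.02253 − 1.96 × 0.01096)/0.01095 = 0.09; power 54%.
- n = 825: (0.02253 − 1.96 × 0.01266)/0.01265 = −0.18; power 43%.

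**6. Full grid (both means, all three SDs).**

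| Shift | n per group | Power, value | Power, flag |
|---|---|---|---|
| 2 mmHg | 825 | 53–72% | 16–21% |
| 2 mmHg | 1,100 | 65–83% | 20–27% |
| 3 mmHg | 825 | 86–97% | 32–43% |
| 3 mmHg | 1,100 | 94–99% | 40–54% |
| 4 mmHg | 825 | 98% or more | 52–68% |
| 4 mmHg | 1,100 | over 99% | 64–80% |
| 5 mmHg | 1,100 | over 99% | 84–94% |

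For shifts of 2 to 3 mmHg the smallest loss is 32 percentage points (2 mmHg, mean 132, SD 20, n = 825: 53% against 21%). At 5 mmHg with n = 1,100 the loss falls to 6 to 16 points.

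**7. Smallest shift with 80% power (mean 132, SD 18).** For the value: (1.96 + 0.84) × 0.768 = 2.15 mmHg at n = 1,100, against 4.03 mmHg for the flag. At n = 825 it is 2.48 against 4.62 mmHg.

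**8. Sensitivity to missing readings (assumed shares).** Mean 132, SD 18, 3 mmHg, n = 1,100: if 20% to 40% of patients have no reading and are counted as not above 160 mmHg, the flag has 45% to 35% power, and the value among those with a reading has 94% to 86%. The plan's general presence/absence convention would allow that count but does not state it for this row.

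**The case against.** The strongest case against the point is that the row exists to supply a HAS-BLED item, where a cut is needed, and that it is a secondary outcome. Section 9.7.1 says EMR variables are defined so as to reduce missingness, and section 9.9 warns that EMR data are partly missing and not recorded in a standardised way. A continuous SBP would be available only for patients with a reading. If 60% have one (an assumption; 495 to 660 per group), power on the value at 2 mmHg falls to 35% to 62%. The SBP distribution, the shift and the 5% test are also not the plan's. These limits stand. They do not remove the advantage of the value at 2 to 3 mmHg, but they mean the fix must include a count of readings.

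Four stronger readings are tempting and not supported:
- *That the reading is discarded.* The documents only leave the value column empty, as they do for several other yes/no items. Text and table content on covariates and Objective 3 is redacted or not shown.
- *That differences below 160 mmHg are invisible.* A shift of the whole distribution does move the flag, and SBP >120 mmHg enters the hypertension-history row, although bluntly and not as a measure of control.
- *That an imbalance would be reported as balance.* No test or threshold is visible. A result such as 6.0% against 8.2% would be printed, and its interpretation is left open.
- *That any real shift would usually be missed.* At 4 mmHg or more with 1,100 per group, the flag would usually show it.

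**Conclusion.** The point holds as a limited loss of information. In the readable text, blood pressure control reaches the outputs only as a flag above 160 mmHg, although the reading must be obtained to set that flag and the plan already keeps creatinine both as a cut and as a value. For differences of 2 to 3 mmHg the flag gives up at least 32 percentage points of power on the grid used.

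The size depends on the assumed SBP mean and SD, complete readings and a 5% test. A higher mean favours the flag: at an assumed mean of 140 mmHg and a 3 mmHg shift the loss is about 21 to 32 points. Nothing in the documents shows that 2 to 3 mmHg would matter as confounding, so this concerns what the study can detect. It does not show that the study's conclusions would be wrong.

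**What to change.** - **Table 1:** in the uncontrolled hypertension row, enter 'The value' for the most recent pre-index SBP. Keep >160 mmHg as the HAS-BLED component.
- **Table 9:** report by drug group the number of patients with a reading, the mean and SD of SBP, and the between-group difference with its 95% CI.
- **Objective 3:** where the exposure models include blood pressure, enter SBP as a continuous covariate and state how patients without a reading are handled. Only one sentence of that specification is readable, so this is conditional on what the rest contains.

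No further patients or readings are needed, because the flag already requires the latest one. The cost is one table entry, one row of output and a missing-reading rule. The downsides are one more comparison and a result limited to patients with a recorded reading.

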**Table 2** **Components of HAS-BLED bleeding risk score\***

[figure not shown]
HAS-BLED item	Points
Hypertension (uncontrolled)	1
Abnormal renal and liver function (1 point each)	1 or 2
Stroke	1
Bleeding history or predisposition (anemia)	1
Labile INR	1
Elderly	1
Drugs or alcohol (1 point each)	1 or 2

[figure not shown]
\*HAS-BLED score is calculated by adding the specified points for each of the conditions listed. [\[R10-6394\]](#)

[figure not shown]

[figure not shown]

[figure not shown]

[figure not shown]

[figure not shown]

[figure not shown]

[figure not shown]

[figure not shown]

[figure not shown]

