## **9.11 SUBJECTS**

### **9.11.1 Study group**

The main cohort will consist of patients with NVAf at risk for stroke initiating warfarin and dabigatran, from October 2010 through December 2014.

Inclusion criteria:

- Initiation of an oral anticoagulant is defined by a dispensing of an anticoagulant medication (warfarin or dabigatran) in the source data, with no dispensing of any oral anticoagulant in the prior 12 months. The date of that dispensing will be defined as the index date for that initiation.
- At least one ICD-9 diagnosis code of 427.31 (atrial fibrillation) at any time prior to and including the index date
- At least 12 months (365 days) continuous enrollment, defined as  $\leq 32$  days enrollment gap using enrollment and disenrollment dates, preceding the index date
- 18 years of age and older at index date
- CHA2DS2-VASc score  $\geq 1$

Exclusion criteria:

- Patients with a nursing home stay during baseline
- Patients with missing or ambiguous age or sex information.
- Patients with a dispensing of any oral anticoagulant during the 12 months preceding and including the index date
- Patients with documented evidence of valvular disease defined as at least 1 inpatient or outpatient ICD-9 Dx code of [\[R11-4334\]](#)  
394.x (diseases of mitral valve)  
395.x (diseases of aortic valve)  
396.x (diseases of mitral and aortic valve)  
397.x (diseases of other endocardial structures)  
398.9x (other and unspecified rheumatic heart diseases)  
V42.2 (heart valve replaced by transplant)  
V43.3 (heart valve replaced by a mechanical device/prosthesis)  
OR  
ICD-9 procedure code 35.1x (open heart valvuloplasty without replacement), 35.2x (replacement of heart valve) [\[R03-1232\]](#)  
OR  
one of the following CPT codes:  
33660-33665 (atrioventricular valve repair)  
33400-33403 (aortic valve valvuloplasty)  
33420-33430 (mitral valve repair/valvuloplasty/replacement)  
33460 (valvectomy, tricuspid valve, with cardiopulmonary bypass)  
33463-33468 (tricuspid valve repair/valvuloplasty/replacement)  
33475 (replacement, pulmonary valve)

33496 (prosthetic valve dysfunction repair)  
0257T (implantation of catheter-delivered prosthetic aortic heart valve; open thoracic approach)  
0258T (transthoracic cardiac exposure for catheter-delivered aortic valve replacement; without cardiopulmonary bypass)  
0259T (transthoracic cardiac exposure for catheter-delivered aortic valve replacement; with cardiopulmonary bypass)  

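### HAS-BLED mixes recorded and calculated scores in one variable, and the visible text lists no EMR stroke item for the calculated ones; one scoring rule for every patient would be a cheap improvement

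*Combined protocol and SAP*

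**What the plan says.** HAS-BLED is a secondary outcome (section 9.3.2.2). Table 1 defines it as "As recorded (if recorded) or calculated from EMR data"; the text that follows in the same cell is redacted. A source indicator is kept, "Recorded/ calculated /none", and the quantity analysed is the value itself.

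The footnote to Table 2 gives the scoring rule: "HAS-BLED score is calculated by adding the specified points for each of the conditions listed". The items include stroke (1 point) and labile INR (1 point).

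Table 1 marks two rows as HAS-BLED inputs: uncontrolled hypertension, and antiplatelets or NSAIDs. It also has rows for renal function, liver function, bleeding and alcohol. For cerebrovascular history it has prior TIA, defined as "Any note of TIA". INR is one value, "Closest to the index date".

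Section 9.11.1 admits initiators "with no dispensing of any oral anticoagulant in the prior 12 months", in both exposure groups. Section 9.7.1 (Objective 1) summarises continuous characteristics by group as a mean with its SD, and the shell of Table 9 has one column per group. Objective 3 uses logistic regressions of exposure on covariates.

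**The concern.** The study exists to find EMR characteristics that remain unbalanced after propensity score matching. A composite serves that purpose only if it means the same thing in every patient. Here the source of the score, and possibly its item content, depends on whether someone happened to write a score in the record.

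Two things could go wrong:

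- **Lost contrast.** If calculated scores leave out stroke, a true difference in stroke history between groups barely reaches the score. This needs no difference in recording between groups.
- **Spurious contrast.** If recorded and calculated scores differ on average, and recorded scores are more common in one group, part of the mean difference reflects documentation practice and not bleeding risk.

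**Working it through.** The documents give no HAS-BLED figure to reproduce, so the check is a mapping of items followed by a bound on the effect.

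**Item mapping (Table 2 against the visible rows of Table 1)**

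| Table 2 item | Points | Visible EMR source |
|---|---|---|
| Uncontrolled hypertension | 1 | Own row |
| Abnormal renal / liver function | 2 | Own rows |
| Stroke | 1 | None; TIA only |
| Bleeding or predisposition, with anemia named | 1 | Bleeding row; anemia not named |
| Labile INR | 1 | One INR value |
| Elderly | 1 | No row, but age is known for every patient |
| Drugs / alcohol | 2 | Antiplatelet/NSAID row; alcohol row, coded "Alcohol use (any); No use" |

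Maximum by Table 2: 1 + 2 + 1 + 1 + 1 + 1 + 2 = 9. Without stroke and labile INR: 9 − 2 = 7. With stroke restored and labile INR left out: 8.

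**Lost contrast.** Suppose stroke is counted in recorded scores but not in calculated ones, and a share r of scores is recorded in both groups. A true stroke difference d then appears as r × d. With assumed d = 0.05 and r = 0 to 0.30, it appears as 0 to 0.30 × 0.05 = 0.015 points.

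**Spurious contrast.** Let g be the mean recorded-minus-calculated gap, equal in both groups and unrelated to which patients have a recorded score. Each group mean shifts by its recorded share times g, so the artefact in the difference is (r_dabigatran − r_warfarin) × g. The documents give neither the shares nor the gap, so the values below are assumed.

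| Difference in recorded share | g = 0.05 | g = 0.10 | g = 0.20 | g = 0.30 |
|---|---|---|---|---|
| 0 | 0 | 0 | 0 | 0 |
| 10 points | 0.005 | 0.01 | 0.02 | 0.03 |
| 20 points | 0.01 | 0.02 | 0.04 | 0.06 |
| 30 points | 0.015 | 0.03 | 0.06 | 0.09 |

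If omitted stroke is the only source of the gap, g equals stroke prevalence. At an assumed 10% to 20%, g is 0.1 to 0.2.

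**Scale for comparison.** Section 9.5 gives 20,000 × 5.5% = 1,100 linked patients per group, which reproduces. The SE of a mean difference is SD × √(2/n):

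- SD 1.0 (assumed): 1.0 × √(2/1,100) = 0.043.
- SD 1.2 (assumed): 1.2 × √(2/1,100) = 0.051.
- 95% half-width (1.96 × SE): 0.08 to 0.10.

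With the 15,000 per group given in the abstract, n = 15,000 × 5.5% = 825 and the SE is 0.049 to 0.059.

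The 20-point, 0.2-gap case gives 0.04, just under one SE. Only the corner of the grid (0.09) approaches the 95% half-width.

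**The case against.** The strongest reply is that the gap is not proven. The sentence after the HAS-BLED definition is blacked out, and the section on covariates (9.3.3) is not readable. The rule refers to EMR data in general and not to the rows of Table 1; age also lacks a row and is plainly available. A reader might infer that the score cannot be calculated at all, but the documents do not show that. What stands is narrower: the outcome lists in 9.3.2.1 and 9.3.2.2, which show no redaction, name inputs for HAS-BLED but no stroke item, and no visible rule says how stroke is scored.

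Labile INR is a weak point to press. Patients had no oral anticoagulant dispensed for 12 months, so the item should rarely score in either group.

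A reader might also infer that any between-group difference is partly artefact, or that it could reach 0.10 or 0.20 points. The first fails because the expected artefact is zero when recorded shares are equal and recording is unrelated to the omitted items. The second needs gaps of 0.5 or 1.0 point with a 20-point difference in shares; omitting stroke supplies at most about 0.2 at the assumed prevalence. The differences over anemia and alcohol could move the gap either way, and the documents do not size them. Nor do they say who recorded a score, or how completely.

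Finally, the source indicator already makes separate reporting possible, and several components are outcomes in their own right, so the objectives do not hang on the composite. Both statements are true. However, no visible text plans separate reporting, and stroke is the component without its own listed EMR outcome.

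**Conclusion.** The point holds as a cheap improvement. It is not a demonstrated bias. The visible definition puts two quantities that may be built differently into one value, with no visible EMR stroke item behind the calculated one.

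The more dependable consequence is lost contrast: if calculated scores omit stroke, a true 0.05 difference appears as 0 to 0.015 when 0% to 30% of scores are recorded. The artefact from unequal recording is conditional and probably small, about 0.04 points against an SE of 0.043 to 0.051. Recorded shares, gap, stroke prevalence and SD are all assumptions. The conclusion would change if the redacted text already scores stroke from the EMR and applies one rule to all patients.

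**What to change.** For the comparisons under Objectives 1 and 3:

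1. Add to Table 1 a prior-stroke item: any EMR note of stroke up to and including the index date.
2. Calculate HAS-BLED from EMR components by one stated rule for every patient, whether or not a score was recorded.
3. Leave the labile-INR item out in both groups and label the result a modified HAS-BLED with a maximum of 8.
4. Use the existing source indicator to tabulate recorded scores separately by exposure group, with the share recorded in each.

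The cost is one extra EMR item and a change of wording. The downside is that the score becomes a labelled modification and recorded scores leave the main comparison. If the redacted text already covers any of these steps, that step needs only to be confirmed.
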